4. AIMS AND OBJECTIVES

Aim 1: To demonstrate the feasibility of performing a trial of pSAE in trauma patients with splenic injuries (see section 8 “Outcomes”).

Objective 1a: To demonstrate that at least 50% of eligible patients can be enrolled into a randomized clinical trial.

Objective 1b: To demonstrate that successful follow-up at 30 days will be obtained in at least 80% of enrolled patients.

Aim 2: To evaluate clinical outcomes in order to identify endpoints for a larger trial (see section 8 “Outcomes”).

[figure not shown]
Objective 2a: To compare clinical outcomes of pSAE using coils versus vascular plugs.

Objective 2b: To compare technical outcomes of pSAE using coils versus vascular plugs.

Objective 2c: To conduct a cost analysis of using coils versus vascular plugs.

5. DESIGN AND INTERVENTION

[figure not shown]
Randomized clinical trial. Patient flow is summarized in the CONSORT diagram below.

Study Calendar:

We anticipate this pilot project to take 16 months to complete. December 2018: IRB approval, training and education of study staff, training and education of trauma and interventional radiology physicians; January 2019 – December 2019: patient enrollment; data collection and monitoring; January 2020 – February 2020: Data analysis and data monitoring; March - April 2020: Final data analysis; manuscript preparation and submission.

ELSA Trial Timeline

6. PATIENTS, RECRUITMENT, AND RANDOMIZATION

6.1 Setting

This study will be performed at the University of Alabama Hospital.

6.2 Study population

6.2.1 Inclusion criteria

- a) ≥ 18 years of age
- b) Trauma resulting in grade III or higher splenic injury on contrast-enhanced CT as defined by the AAST guidelines
- c) Splenic injury to be treated by non-operative management as decided by attending trauma surgeon and interventional radiologist
- d) Patient will undergo proximal splenic artery embolization as decided by the attending interventional radiologist

6.2.2 Exclusion criteria

- a) Inability to obtain informed consent
- b) Uncorrectable coagulopathy
- c) Patient is immunocompromised
- d) Pregnant
- e) Breast-feeding
- f) Non-English speakers
- g) Prisoners

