6.3 Recruitment

An attending trauma surgeon will evaluate all trauma patients. Patients with a confirmed grade III or higher splenic injury on contrast-enhanced CT will be considered for entry into the study. Typically, hemodynamically unstable patients or stable patients with additional injuries that would require abdominal surgery are managed operatively while all others are candidates for non-operative management. The decision to proceed with

splenic artery embolization will be made by an attending interventional radiologist in conjunction with the attending trauma surgeon.

Clinicians will be assisted by research associates (RAs) from the Alabama Resuscitation Center (ARC), who are available 24 hours per day, and will screen all patients with grade III (and higher) splenic injuries for entry into the study. The RAs will discuss the protocol with the patient and/or their representative, and notify the trauma team if they are prepared to participate. The RA will notify both the attending trauma surgeon, and the interventional radiologist, that the patient is potentially eligible for the study. Once the attending interventional radiologist deems the patient an appropriate candidate for SAE, the interventional radiology team will screen the patient for eligibility. Once deemed eligible, informed consent for the procedure *and* the study will be obtained by the interventional radiology service from either the patient or their legally-authorized representative. If the patient is unable to consent for themselves *and* the legally-authorized is not physically present, the patient will be considered excluded from the study. All study and consent discussions will take place in a private room, away from other patients, so that conversations cannot be overheard and potential subjects cannot be publicly identified.

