8. OUTCOMES

Aim 1: Demonstrate feasibility by meeting enrollment and follow-up goals.

Objective 1a: Enroll at least 50% of eligible patients (50 patients total; 25 patients per arm)

Objective 1b: Obtain follow-up in at least 80% of enrolled patients

Aim 2: Assess for similarities and differences between the groups regarding clinical outcomes.

Objective 2a: Compare clinical outcomes of pSAE using coils versus vascular plugs (splenic salvage, immediate/delayed complications, patient length of stay, and post-embolization transfusion requirements)

Objective 2b: Compare technical outcomes of pSAE using coils versus vascular plugs (technical success (defined as the ability to access and embolize the mid-splenic artery), intra-procedural complications, necessity of a secondary embolic to obtain satisfactory hemostasis, and intra-procedural radiation doses)

Objective 2c: Conduct cost analysis of using coils versus vascular plugs (room time, equipment such as catheters, wires, and sheaths, and the cost of the embolic agent itself)

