10. RECRUITMENT TARGETS

Our group performs approximately 100 SAEs in a 12 month period. Thus, we will consider having enrolled at least 50% of the SAE patients (50 patients total; 25 patients/arm) as success.

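### Read literally, Objective 1a's share of eligible patients leaves out those who could not be consented, and the 50-patient count and all-SAE criterion are not a secure safeguard

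*Combined protocol and SAP*

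**What the plan says.** Section 11 makes feasibility the primary outcome. Section 4 states Objective 1a as "To demonstrate that at least 50% of eligible patients can be enrolled into a randomized clinical trial". Section 8 repeats it with a count attached: "Enroll at least 50% of eligible patients (50 patients total; 25 patients per arm".

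Section 6.2.2, item (a), excludes patients for "Inability to obtain informed consent". Section 6.3 gives this content: if the patient cannot consent and the legally authorized representative is not there in person, "the patient will be considered excluded from the study". The same section places consent after the eligibility decision: "Once deemed eligible, informed consent for the procedure" and for the study is then sought.

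Section 10 judges success on another base. It says "Our group performs approximately 100 SAEs in a 12 month period", and then "we will consider having enrolled at least 50% of the SAE patients (50 patients total; 25 patients/arm) as success".

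Section 5 plans enrolment from January to December 2019, which is 12 months. The end of section 14.4 says enrolment will go on until 25 patients in each arm have at least three months of follow-up.

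**The concern.** A patient who meets an exclusion criterion is not eligible. If being impossible to consent is an exclusion, a patient lost for that reason leaves the denominator of Objective 1a instead of counting as eligible but not enrolled. The percentage then describes acceptance among people who could be asked, directly or through a representative. It says nothing about how many clinically suitable patients could not be asked at all.

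This matters because the pilot is meant to show that a larger trial is feasible (section 3). Planning that trial requires the number of clinically suitable patients who can be entered. A pass on the literal percentage could be reported when fewer than half of them were.

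**Working it through.** **The plan's own figure.** Section 10 gives about 100 SAEs in 12 months and a 50% threshold: 0.50 × 100 = 50, the stated target. The 50 therefore rests on all SAE patients as the base. It equals half of the eligible patients only if all of the roughly 100 are eligible.

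**Inputs that must be assumed.** The documents give no rate of incapacity, refusal or consent. Let *u* be the share of clinically qualifying patients who cannot consent and have no representative present, and *a* the acceptance rate among the rest. Take 100 clinically qualifying patients in 12 months and, at first, no losses to the other exclusions.

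**Formulas.**
- Enrolled = 100 × (1 − *u*) × *a*
- Literal denominator = 100 × (1 − *u*), so the literal rate = *a*, whatever *u* is
- Share of clinically qualifying patients = (1 − *u*) × *a*
- Months to enrol 50 = 12 × 50 / enrolled

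| *u* | *a* | Enrolled in 12 months | Literal rate | Share of clinically qualifying | Months to 50 |
|---|---|---|---|---|---|
| 0.20 | 0.80 | 64 | 64/80 = 80%, pass | 64/100 = 64%, pass | 9.4 |
| 0.30 | 0.60 | 42 | 42/70 = 60%, pass | 42/100 = 42%, fail | 14.3 |
| 0.40 | 0.70 | 42 | 42/60 = 70%, pass | 42/100 = 42%, fail | 14.3 |
| 0.50 | 0.80 | 40 | 40/50 = 80%, pass | 40/100 = 40%, fail | 15.0 |

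**When the verdict reverses.** The literal rate passes and the clinical share fails when *a* ≥ 0.50 and *u* > 1 − 0.50/*a*. That means *u* above 1 − 0.50/0.60 = 17% at 60% acceptance, above 1 − 0.50/0.70 = 29% at 70%, and above 1 − 0.50/0.80 = 37.5% at 80%.

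**Does the count of 50 catch it?** Within 12 months, yes: 42 and 40 both fall short of 50. If enrolment continues as section 14.4 allows, the 42-per-year cases reach 50 at 12 × 50/42 = 14.3 months. From then on the count alone no longer shows the shortfall.

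**Is the all-SAE base equivalent?** Only if no one is lost to the other criteria. Suppose 20% of the 100 SAE patients fail a clinical criterion, with *u* = 0.20 and *a* = 0.70. Enrolled = 100 × 0.80 × 0.80 × 0.70 = 44.8. Against the 80 clinically qualifying patients this is 44.8/80 = 56% (pass). Against all SAE patients it is 44.8% (fail). Section 10 therefore combines consent failure with clinical ineligibility and cannot separate them.

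**The case against.** The strongest reply is that sections 8 and 10 already count these patients. A patient who has SAE but could not be consented stays among the roughly 100 and works against the target of 50. With 100 qualifying patients and a 12-month window, the count gives the same verdict as the clinical denominator in every row of the table. This stands. A reader might infer that Objective 1a is unable to reveal a consent problem at all, and the documents do not support that. The protection is still insecure. Section 10 uses a different base from the objective, which sections 4 and 8 both state in terms of eligible patients, and nothing says which governs. Section 14.4 also removes the time limit that makes the count informative.

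A reader might also infer that refusals drop out too, making the rate 100% by construction. The text points the other way. Item (a) speaks of inability, section 6.3 seeks consent after eligibility, and section 6.4 lists meeting the criteria and giving consent as separate steps. Refusals after eligibility most plainly stay in the denominator. Some ambiguity remains, because section 6.3 has research associates discuss the study and report willingness before the interventional radiology team screens for eligibility. A patient who declines at that stage might never be recorded as eligible.

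The consent-step rule in section 6.3 could also mean not enrolled rather than ineligible. That is a fair reading of that sentence, but it does not remove item (a) from the exclusion list.

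Finally, a reader might infer that consent is the main obstacle to enrolment. The documents do not say so. Intubation and GCS appear in section 9 only as data fields, representatives may consent, and research associates are available around the clock. The CONSORT diagram is not shown in the text available, so it may report consent failures separately.

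**Conclusion.** The concern holds in limited form. On the literal wording of sections 4, 6.2.2, 6.3 and 8, the primary accrual percentage does not change with the share of patients who cannot be consented. The 50-patient count and the all-SAE criterion would show the loss within the planned 12 months. They are not a secure safeguard, because the denominators conflict and enrolment may be extended.

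The size depends on rates that the documents do not give. At an assumed 40% unable to consent and 70% acceptance, the result is 70% (pass) against 42% (fail). At 20% and 80%, both measures pass and the definition does not matter for the verdict. These figures assume 100 clinically qualifying patients a year and no other exclusions. What the documents establish is that the primary success criterion lacks a single defined value, and that following one of its stated forms can give the wrong feasibility conclusion.

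**What to change.** Judge the 50% criterion on one denominator: all patients who meet inclusion criteria a–d and none of exclusions b–g during the planned 12-month enrolment window. Treat consent as a condition of enrolment, not of eligibility. Count patients who could not consent and had no representative present, who declined, or who were not approached as eligible but not enrolled, and report each reason separately. Patients enrolled after month 12 under section 14.4 would not count towards this criterion.

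Align sections 6.2.2, 6.3, 8 and 10 with this definition. Section 4 can keep its wording once eligible is defined.

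The cost is the rewording and one reason field in the log of the screening that the research associates already do. The reported enrolment rate may be lower. Who may be enrolled does not change.

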6.3 Recruitment

An attending trauma surgeon will evaluate all trauma patients. Patients with a confirmed grade III or higher splenic injury on contrast-enhanced CT will be considered for entry into the study. Typically, hemodynamically unstable patients or stable patients with additional injuries that would require abdominal surgery are managed operatively while all others are candidates for non-operative management. The decision to proceed with

splenic artery embolization will be made by an attending interventional radiologist in conjunction with the attending trauma surgeon.

Clinicians will be assisted by research associates (RAs) from the Alabama Resuscitation Center (ARC), who are available 24 hours per day, and will screen all patients with grade III (and higher) splenic injuries for entry into the study. The RAs will discuss the protocol with the patient and/or their representative, and notify the trauma team if they are prepared to participate. The RA will notify both the attending trauma surgeon, and the interventional radiologist, that the patient is potentially eligible for the study. Once the attending interventional radiologist deems the patient an appropriate candidate for SAE, the interventional radiology team will screen the patient for eligibility. Once deemed eligible, informed consent for the procedure *and* the study will be obtained by the interventional radiology service from either the patient or their legally-authorized representative. If the patient is unable to consent for themselves *and* the legally-authorized is not physically present, the patient will be considered excluded from the study. All study and consent discussions will take place in a private room, away from other patients, so that conversations cannot be overheard and potential subjects cannot be publicly identified.

6.4 Randomization

[figure not shown]
After meeting the above criteria and obtaining informed consent, the patient will be randomized to either the coil arm or arm. Randomization will occur by sealed numbered envelopes. The sealed envelopes will be located in the Interventional Radiology Reading Room in the Heart and Vascular Center (6th floor, North Pavilion). This is a secure area requiring badge access at all times.

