Local anesthesia will be achieved with lidocaine. The right common femoral artery is the most commonly used vascular access for splenic artery embolization but the left common femoral artery may be used for certain patients. No radial artery access will be used. Regardless, the artery is accessed under direct sonographic guidance with a micro-puncture set. The micro-puncture set is then exchanged for a vascular sheath over a wire and attached to a heparinized saline flush. A celiac axis angiogram is then performed. The attending interventional radiologist will choose the diagnostic catheter based on his/her preference. The attending interventional radiologist will review the celiac angiogram to identify an appropriate landing zone in the mid-splenic artery distal to the origin of the dorsal pancreatic artery but proximal to the origin of the pancreaticomagna artery in order to preserve collateral flow to the spleen via the transverse pancreatic artery. The vessel's diameter at this location will be measured and recorded. For patients randomized to coil embolization, a high-flow micro-catheter is navigated to the location of embolization with the assistance of a micro-wire. The micro-wire-micro-catheter combination will be left to the discretion of the attending interventional radiologist. Once the micro-catheter is in place, a splenic angiogram will be performed. Coil embolization will then proceed per the manufacturer's instructions for use until satisfactory hemostasis is achieved. For patients randomized to vascular plug embolization, the appropriately-sized catheter or sheath is advanced to the location of embolization. The tools used to access the mid-splenic artery will vary depending on the operator's experience and patient anatomy. Once the catheter is in place, a splenic angiogram will be performed. Vascular plug embolization will then proceed per the manufacturer's instructions for use until satisfactory hemostasis is achieved. For both coil and vascular plug embolization, absence of flow at the level of the embolic agent in the mid-splenic artery will serve as the endpoint for satisfactory hemostasis. Regardless of the embolic used the interventional radiologist will perform intermittent angiograms (one per minute) to determine if stasis has been achieved. The time to hemostasis will be recorded. If hemostasis is not achieved after 15 minutes, then a secondary embolic can be employed. If a secondary embolic agent such as particles or gelfoam is needed for patients in either group, this will be recorded. All potential secondary embolic agents are FDA-approved devices and commercially available. Additionally, if the operator is unable to navigate into the mid-splenic artery with the necessary tools to perform the

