
required embolization, this will also be recorded. In this circumstance, the procedure will be recorded as a technical failure and the operator will then proceed to treat the patient as he/she deems appropriate. Catheters and wires will be removed after hemostasis is obtained in the mid-splenic artery. As is standard at our institution, the arteriotomy will be closed with a FDA-approved, commercially available vascular closure device, if possible. If the patient isn't a candidate for a vascular closure device, then hemostasis at the arteriotomy will be obtained with manual pressure, as is standard at our institution.

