7.5 Patient Follow-up

Patients will be followed for 30 days +/- 3 days after pSAE. For patients still admitted to the hospital, data will be collected from the medical record. For discharged patients with follow-up at UAB, data will be collected from the medical record. For discharges patients without follow-up, the program manager/research coordinator will contact the patient via telephone to collect relevant data (see section 9 "Data Collection").

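### Arms appear to be assigned before the celiac angiogram that shows whether proximal embolization can go ahead, and the plan has no rule for randomized patients who do not receive it

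*Combined protocol and SAP*

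**What the plan says.** Section 6.4 sets the point of assignment: "After meeting the above criteria and obtaining informed consent, the patient will be randomized". Under section 6.3, consent to the procedure and to the study is taken together, before the procedure; it "will be obtained by the interventional radiology service from either the patient or their legally-authorized representative". The Protocol Summary lists randomization ahead of embolization.

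Inclusion criterion d (section 6.2.1) reads: "Patient will undergo proximal splenic artery embolization as decided by the attending interventional radiologist".

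In section 7.3 the order is arterial access, celiac angiogram, landing zone and vessel diameter, then device. Access is femoral: "No radial artery access will be used". The attending radiologist "will review the celiac angiogram to identify an appropriate landing zone in the mid-splenic artery", between two named pancreatic branches. Only after that does the text mention the arm, as something already settled: "For patients randomized to coil embolization, a high-flow micro-catheter is navigated to the location of embolization".

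If the operator cannot navigate into the mid-splenic artery, "the procedure will be recorded as a technical failure and the operator will then proceed to treat the patient as he/she deems appropriate". The Protocol Summary and section 8 define technical success as being able to embolize that segment; the Summary adds that it must be done with the assigned device. Section 7.5 times follow-up from the procedure: "Patients will be followed for 30 days +/- 3 days after pSAE". Section 11 names no analysis population.

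**The concern.** Criterion d is a decision made before access and angiography. It is a forecast that proximal embolization will happen, and the angiogram is where the forecast is tested. A patient may turn out to have no usable femoral access or no suitable landing zone, may be judged on the angiogram to need something else, or may go to surgery first. If the envelope is already open, that patient belongs to an arm although neither device was tried.

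Two things follow. Such patients add outcomes that say nothing about coils against plugs, yet they can be scored as technical failures of the assigned device. And with no written rule, study staff who know the arm would decide case by case whether to keep, drop or replace them. Aim 2 exists to choose endpoints for a larger trial, so distorted or missing technical outcomes weaken the information that the pilot is meant to supply.

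**Working it through.** **Order of events.** Sections 6.3 and 6.4 give eligibility, consent, then randomization. Section 7.3 gives access, angiogram, landing zone and diameter, then device-specific navigation. It contains no randomization step and treats the arm as known once the diameter has been measured. The natural reading is that assignment comes before the procedure. This is an inference: section 6.4 fixes an earliest point and not an exact one.

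**What covers a randomized patient without proximal embolization?**
- The technical-failure rule in section 7.3 addresses failed navigation only.
- The outcome definitions in the Protocol Summary and section 8 would make any such patient a non-success, whatever the reason.
- The procedure variables in section 9 include technical success but no item for embolization not performed, or why.
- The follow-up window in section 7.5 has no start date for this patient.
- The continued-enrollment sentence in section 14.4 is framed around loss to follow-up, not non-receipt of the procedure.

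**Plan's own figure.** Section 10: 50% × about 100 procedures a year = 50 patients, and 50 / 2 = 25 per arm. This reproduces. The plan gives no power, effect size or standard deviation.

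**Size.** Let f be the share of randomized patients who do not receive proximal embolization. The documents give no value; 5-15% is an assumption, taken as equal in both arms.

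*Outcomes that every patient has (splenic salvage, length of stay, transfusion).* If untreated patients show no difference between arms, the observed difference is (1 − f) times the true one. The required size grows by 1/(1 − f)², so 50 patients act like 50 × (1 − f)².

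*Device-level outcomes (time to hemostasis, device cost).* Untreated patients have no value, so 50 × (1 − f) remain.

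| f | Untreated, 50f | Effective size, 50(1 − f)² | With device-level data, 50(1 − f) |
|---|---|---|---|
| 5% | 2.5 | 45.1 | 47.5 |
| 10% | 5 | 40.5 | 45 |
| 15% | 7.5 | 36.1 | 42.5 |

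*Power illustration.* Take two-sided alpha 0.05 (section 11 does not state sidedness), 25 per arm, a normal approximation and an assumed true difference of 0.8 SD. Power is 80.7% at f = 0, 76.6% at 5%, 72.1% at 10% and 67.2% at 15%.

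*Technical success.* One patient is 1/25 = 4 percentage points of an arm's rate.

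**The case against.** **The order is not stated.** This stands. Section 6.4 does not say that the envelope is opened at once, and the figures that might settle it are not shown. A reader might infer that the protocol mandates assignment immediately after consent; the text does not go that far. If practice already differs, section 6.4 needs a sentence saying so.

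**Criterion d already screens.** It does in part. The radiologist must have decided on proximal embolization, and the trauma surgeon's part in choosing non-operative management (criterion c, section 6.3) filters out patients headed for surgery. That should keep f small. It cannot make it zero, because the landing zone is not identified until the angiogram.

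**Navigation failures belong in the comparison.** Correct. A device that cannot be delivered has failed, and excluding such patients would bias technical success. The point concerns only patients lost before device-specific navigation begins.

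**Dilution does not apply to every outcome.** Also correct. A reader might infer that all between-arm differences shrink. For device-level outcomes the patients are missing, so the smaller loss in the last column applies.

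**The comparison is secondary.** It is. Feasibility is the primary outcome, there is no power target, and losses between consent and embolization are themselves useful pilot information.

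**Moving assignment has its own costs.** Operators would see the anatomy first, and section 3 gives tortuosity as a reason plugs may be hard to place, so some could withhold difficult cases. This is a real risk. But while the envelope stays sealed the next arm is unknown, so such selection narrows the population without unbalancing the arms. Later assignment might also force catheter or sheath exchanges that affect Objective 2c. Much of that cost exists already, because the need for a larger plug depends on the diameter measured on the same angiogram.

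**Knowing the arm when choosing the landing zone.** A reader might infer material bias here. The zone is bounded by two named branches, which limits the scope for it, so the conclusion does not rest on this.

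**Conclusion.** The point holds in a limited form. On the natural reading, arms are assigned before it is known whether proximal embolization can proceed. Nothing says how to score, follow or analyse a randomized patient in whom it does not. Such patients would count as technical failures of a device that was never tried.

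At an assumed 5-15%, the loss is from 50 to an effective 45-36 for outcomes that all patients have, and to about 47-42 patients for device-level outcomes. These figures rest on the assumed rate, on equal losses in both arms and, for the dilution, on no arm difference among untreated patients. Because the comparisons are secondary in an unpowered pilot, this is a worthwhile low-cost improvement. It does not threaten the primary aim.

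**What to change.** Amend section 6.4 to say that the next envelope is opened after femoral access and the celiac angiogram, once the operator has recorded that proximal embolization will proceed and has recorded the landing zone and vessel diameter, and before any device-specific navigation. Add that:

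- expected difficulty with one device is not a reason to withhold randomization;
- navigation failures after assignment stay in technical success;
- all randomized patients are analysed as randomized (section 11);
- consented patients who are not randomized are logged with the reason and reported separately from the number randomized under Objective 1a.

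The cost is an amendment to these sections and the flow figure, a log, and a short pause during the procedure to obtain the envelope, which section 6.4 keeps in the reading room. The main downside is that operators might hold back patients with difficult anatomy, which would narrow generalizability. The logged reasons should be reviewed for this.
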